• Participants with medically documented risk factors for severe COVID-19 disease will be excluded from the study and the occurrence of 2 cases of severe COVID-19 disease will trigger the hold of the whole Phase 1 study.

Participants will receive close medical supervision and medical assessments (eg, laboratory testing) during the study.

The investigational CV2CoV vaccine is currently in an early stage of clinical development and vaccine efficacy, immunogenicity, and safety have not yet been demonstrated in humans. Considering the risk mitigation strategies, measures taken, and planned to be taken to minimize risk to participants in this Phase 1 clinical trial, the potential risks associated with the investigational vaccines are considered acceptable.

2 Study Objectives and Endpoints

The study objectives and endpoints are described in Table 2-1.

Table 2-1 Study Objectives and Endpoints

Objectives	Endpoints				
Primary – Safety					
To evaluate the safety and reactogenicity of CV2CoV at each dose level in SARS-CoV-2 seropositive healthy adult participants after booster vaccination	Percentage of participants with MAAEs, SAEs, and AESIs from study vaccination through the end of the study (approximately 180 days after the study vaccine administration), each summarized separately				
	Percentage of participants with each solicited local and systemic AE within the 7-day postvaccination period (Days 1 to 7)				
	Percentage of participants with unsolicited AEs up to 28 days after study vaccination, including clinically relevant abnormal laboratory findings				
Secondary – Immunogenicity					
To explore the dose response and effect of CV2CoV at each dose level on neutralizing Ab titers against pseudovirus bearing spike protein from SARS-CoV-2 WT in SARS-CoV-2	GMTs of neutralizing Ab titers against pseudovirus bearing spike protein from either SARS-CoV-2 WT at each collection time point (Days 1, 8, 15, 29, 85, and 180)				
seropositive healthy adult participants after booster vaccination	• Percentage of participants with seroresponse (≥4-fold rise from baseline) at Day 29 after the booster dose				
	GMI from baseline of neutralizing Ab titers against pseudovirus bearing spike protein from SARS-CoV-2 WT at each collection time point (Days 8, 15, 29, 85, and 180)				

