5.9 Study Holding Rules

The study holding rules in Table 5-2 will be applied independently to each dose group.

Table 5-2 Study Holding Rules

Study Holding Rule	Study Holding Rule Description	Number of Participants Needed to Trigger a Study Hold
1a	Death or any life-threatening SAE regardless of causality	≥1
1b	Any non-life-threatening SAE that cannot be reasonably attributed to a cause other than vaccination as per investigator or Sponsor assessment	≥1
1c	Any withdrawal from the study (by investigator or participant request) following a Grade 3 AE	≥1
1d	Any local or general solicited AE leading to hospitalization OR necrosis at the injection site; each with an event onset within the 7-day postvaccination period (Days 1 to 7)	≥1
1e	Severe cases of SARS-CoV-2 infection	≥2
1f	Any same or similar Grade 3 related unsolicited events, including but not limited to the identical MedDRA high-level term	≥2
1g	Same Grade 3 solicited local or systemic AE in an investigational group	>3
1h	Same Grade 3 or above abnormality in prespecified hematological or biochemical laboratory parameters with an event onset by Day 8 (± 1 day) postvaccination, except nonclinically significant lymphopenia	≥3
2a	Any Grade 3 solicited events in an investigational group, with an event onset within the 7-day postvaccination period (Days 1 to 7)	2 out of 3 first exposed participants 3 out of 5 first exposed participants 7 out of 16 first exposed participants 9 out of 22 first exposed participants 11 out of 28 first exposed participants 12 out of 30 first exposed participants (combined younger and older adult age groups)
2b	Any Grade 3 unsolicited AE , that can be reasonably attributed to the vaccination as per Investigator or Sponsor assessment, with an event onset within the 7-day (Days 1 to 7) postvaccination period	2 out of 15 first exposed participants 3 out of 30 first exposed participants (combined younger and older adult age groups)

Study holding rules 1a through 1d will be assessed by the investigators on a continuous basis. Study holding rules will lead to a halting of the entire study, with the exception of study

holding rule 1c, which will lead to halting of the concerned cohort and the next cohorts with higher doses.

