Study holding rules 1e, 1f, 1g, 1h, 2a and 2b will be assessed by the SRT on an ongoing basis. An adaptive Bayesian logistic regression model will be used during SRT meetings (scheduled or ad-hoc according to Table 5-2) to evaluate the posterior probability for the percentage of severe solicited AEs at the current and the next dose (Appendix 13.3). A lower than 50% posterior probability, that the percentage is above the maximal tolerable dose, will be favorable to progress at the next dose. Each study holding rule will be applied per cohort and age group. Based on the historical Phase 1 data from CVnCoV, Moderna and Pfizer mRNA COVID vaccines, the maximum tolerable rate has been set up to 30%.

The SRT will review all available safety data at scheduled time points and at the time when any of the study holding rules are met. A recommendation will be made to the sponsor on whether a cohort or group should be permanently stopped, modified, or continued unchanged. If a study holding rule is met, it will be escalated according to process to the SRT who will decide whether other participants can be enrolled/vaccinated. Medical judgment, taking into account all available safety data at the time of review, should be the basis for decision to continue the study or not.

In the event of a halting of the study, ethical and regulatory authorities will be notified per local requirements.

6 Study Assessments and Procedures

Before any study procedures are performed, all potential participants will be consented using an IRB/IEC-approved ICF. Additional procedural details related to the ICF are provided in Section 9.3. Study assessments will be performed in an outpatient setting at qualified study sites. Due to the ongoing pandemic, safety follow-up visits may be completed via televisits, as permitted by country regulations. In-person visits should be maintained in the study unless there is a public health emergency limiting access to study sites. During such an emergency or extenuating circumstance, televisits can be employed to keep personal access to subjects and ascertain their safety at a high level.

Refer to the SOE table in Appendix 13.1 for a full list of visits and assessments (Table 13-1).

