vomiting, diarrhea

13 Jun 2022

Severe COVID-19: Laboratory-confirmed SARS-CoV-2 infection with any of the following:

- Clinical signs at rest indicative of severe systemic illness (respiratory rate ≥30 per minute, heart rate ≥125 per minute, blood oxygen saturation ≤93% on room air at sea level or partial pressure of oxygen/fraction of inspired oxygen <300 mmHg)
- Respiratory failure (defined as needing high-flow oxygen, noninvasive ventilation, mechanical ventilation, or extracorporeal membrane oxygenation)
- Evidence of shock (systolic blood pressure <90 mmHg, diastolic blood pressure <60 mmHg, or requiring vasopressors)
- Significant acute renal, hepatic, or neurologic dysfunction
- Admission to an intensive care unit
- Death

The genetic sequence of the spike-encoding gene or the genome of SARS-CoV-2 strains will also be evaluated in relation to the vaccine sequence, when available.

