7.8 Safety Review Team

The SRT activities and committee formation will be described in a separate SRT charter.

Cohorts 1 and 2

In the Cohort 1, the SRT will review sentinel Days 1 to 8 safety data (including Day 8 laboratory data) for the 2 μ g and 4 μ g dose in the younger age groups and make recommendations to open the enrollment in the older age group. The SRT will also review sentinel Day 8 safety data for the 2 μ g, 4 μ g, and 8 μ g dose groups and make recommendations to progress to expanded enrollment in the same dose cohort and to begin enrollment in the next higher cohort.

Cohorts 3, 4, 5

The SRT will review sentinel Days 1 to 8 safety data (including Day 8 laboratory data) for the 12 μ g, 16 μ g, and 20 μ g dose groups and make recommendations to progress to expanded enrollment in the same dose cohort. The SRT will review Day 8 safety data for the entire dose group (eg, 12 μ g) and make recommendations to begin enrollment in the next higher dose cohort (eg, 16 μ g).

The SRT will take into consideration the study holding rules in Section 5.9.

The SRT review based on interim analysis data will be performed as described in the SRT charter.

Based on SRT review and recommendations, dose groups may be dropped at any time during the study if an unfavorable safety profile is observed in that group or based on safety or immunogenicity data from other groups.

8 Data Quality Assurance

This study will be conducted according to the ICH E6(R2) risk and quality processes described in the applicable procedural documents. The quality management approach to be implemented in this study will be documented and will comply with the current ICH guidance on quality and risk management. The sponsor assumes accountability for actions delegated to other individuals (eg, contract research organizations).

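### Section 1.2 promises a whole-study hold at 2 severe COVID-19 cases, but Section 5.9 counts them within each group, so one case in each of two groups would not trigger rule 1e

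*Protocol*

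**What the plan says.** Protocol Section 1.2 names vaccine-associated disease enhancement as an important risk for SARS-CoV-2 vaccines. Its list of mitigations includes this one: "the occurrence of 2 cases of severe COVID-19 disease will trigger the hold of the whole Phase 1 study". The count is not restricted to a dose, cohort or age group. The section closes by saying that, in view of the mitigations, "the potential risks associated with the investigational vaccines are considered acceptable".

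Section 5.9 contains the operative rules. In Table 5-2, rule 1e reads "Severe cases of SARS-CoV-2 infection" with a trigger of 2 or more participants. The sentence introducing the table says: "The study holding rules in Table 5-2 will be applied independently to each dose group". A later paragraph says: "Each study holding rule will be applied per cohort and age group". Neither sentence exempts rule 1e. Any met rule other than 1c halts the entire study.

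Three other provisions bear on the point:

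- Rule 1a stops the study at one event: "Death or any life-threatening SAE regardless of causality". Rule 1b does so for one non-life-threatening SAE that cannot reasonably be attributed to something other than vaccination.
- Section 6.6 lets a laboratory-confirmed infection count as severe on a clinical sign alone, for example "blood oxygen saturation ≤93% on room air at sea level".
- Section 7.8 allows the SRT to recommend dropping a dose group "based on safety or immunogenicity data from other groups".

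**The concern.** The two sections agree on the threshold (2) and on the consequence (the whole study stops). They differ on what is counted. Section 1.2 reads as a study-wide count; Section 5.9 counts within groups. A site or SRT following Section 5.9 exactly would record one severe case at 4 µg and one at 12 µg as a count of 1 in each group, with rule 1e not met.

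This matters because Section 1.2 rests its judgement of acceptable risk on the listed mitigations. A disease-enhancement signal need not be confined to one dose level. If cases are spread over doses, the predefined hold does not operate while higher-dose cohorts are still opening, and neither does the unscheduled SRT review that a met rule prompts. The response then depends on discretion at scheduled reviews.

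**Working it through.** **The plan's own figures.** The protocol gives no operating characteristic for rule 1e. The nearest stated figures, in Section 7.2, reproduce: with n=30, P(at least 1 AE) = 1 − 0.95^30 = 78.5% at a 5% rate and 1 − 0.90^30 = 95.8% at 10%.

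**Textual check.** Take one severe case in each of two dose groups in different cohorts, neither meeting rule 1a or 1b.

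| Source | Counting unit | Count | Hold? |
|---|---|---|---|
| Section 1.2 | none stated (whole study) | 2 | yes |
| Section 5.9, sentence introducing Table 5-2 | dose group | 1 and 1 | no |
| Section 5.9, later paragraph | cohort and age group | 1 and 1 | no |

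Such cases are possible. Under Section 6.6 a case is severe on oxygen saturation or a respiratory rate of 30 or more alone. It need not be life-threatening (1a), and an SAE put down to the infection itself need not meet 1b.

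**How often two cases share a group.** Inputs: 30 per dose group and six dose groups (Table 3-1); 10 to 20 per age group within each dose group. Assumption: equal risk for all participants, so the two cases fall at random. For groups of size n_i totalling N,

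P(same group) = Σ n_i(n_i − 1) / [N(N − 1)], which for k dose groups of 30 is 29/(30k − 1).

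| Dose groups filled | N | P(rule 1e met) |
|---|---|---|
| 2 | 60 | 29/59 = 49% |
| 3 | 90 | 29/89 = 33% |
| 4 (before 16 µg opens) | 120 | 29/119 = 24% |
| 5 (before 20 µg opens) | 150 | 29/149 = 19% |
| 6 | 180 | 29/179 = 16% |

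The rows for four and five groups matter most, because Cohorts 4 and 5 open only after data from all participants in the previous cohorts. Cohorts 2 and 3 open on sentinel data, so the first two rows are not decision points. At six groups no dosing is left to hold.

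Counted by cohort and age group, with Cohort 1 pooling 2 and 4 µg:

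| Enrolment complete through | 15/15 age split | 10/20 age split |
|---|---|---|
| Cohort 1 | 49% | 55% |
| Cohort 2 | 27% | 30% |
| Cohort 3 | 18% | 20% |
| Cohort 4 | 13% | 15% |

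**Chance of a trigger by n=120.** The documents give no rate of severe cases outside rules 1a and 1b, so a per-participant risk r is assumed over a range. Study-wide: 1 − F(1; 120, r). Per dose group: 1 − F(1; 30, r)^4. F is the binomial cumulative probability.

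| Assumed r | Study-wide count | Per-dose-group count |
|---|---|---|
| 0.1% | 0.7% | 0.2% |
| 0.5% | 12% | 4% |
| 1% | 34% | 14% |

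**The case against.** The strongest reply is that Section 1.2 is itself current protocol text and tells the reader to hold at two cases, and nothing in Section 5.9 forbids a hold for cases in different groups. On that view the defect is two unreconciled statements rather than a missing trigger. The table supports this to a degree: rules 1g and 2a are worded as applying within an investigational group and 1e is not, which hints at a study-wide intent. But the sentence introducing the table covers all its rules without exception. If a study-wide count was intended, Section 5.9 states the opposite.

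The sentence on cohort and age group is also a weak basis. It sits in the paragraph on the Bayesian model for solicited events, and it cannot hold literally for rules 2a and 2b, which combine the age groups. That is a fair reason to put little weight on the cohort-by-age figures. The gap does not need them, since it exists under the dose-group wording alone.

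The practical reach is limited, and this stands. Fatal and life-threatening cases stop the study singly under 1a. A serious case suspected to be enhancement can do so under 1b. Every confirmed infection is an AESI reportable within 24 hours. Each higher cohort opens only after SRT review, and a met rule also ends in SRT judgement. However, Section 3.2 lists predefined holding rules separately from ongoing SRT review, so discretion is not offered as a substitute for the rule.

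The rates are illustrative. Exclusion criterion 24 removes listed risk factors for severe COVID-19, so the lower end of the range may be nearer the truth. The n=120 calculation also has no time axis: the newest participants may have only about 8 days of follow-up when 16 µg opens. Finally, the SRT charter was not available and may state the counting unit. The protocol would still contradict itself.

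**Conclusion.** The concern holds. Followed as written, Section 5.9 does not deliver the mitigation that Section 1.2 describes when severe cases fall in different groups. This conclusion is textual and does not depend on any assumed rate.

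As to size, for two cases outside rules 1a and 1b at equal risk, the promised hold would be missed in about 76% of placements (90/119) before 16 µg opens and 81% (120/149) before 20 µg opens, counting by dose group. If enhancement rises with dose, cases would cluster and the rule would miss fewer. The absolute effect depends on an undocumented risk: it is small at 0.1% and material at 0.5% to 1%. What is lost is an automatic trigger, not safety oversight.

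It should be fixed in the protocol as written. SAP Section 12 records that the study closed early, so the correction now matters mainly for reporting and for any reuse of these rules.

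**What to change.** Count rule 1e across the whole study. In Section 5.9 and Table 5-2, exempt 1e from both the dose-group sentence and the cohort-and-age-group sentence, and state that severe COVID-19 cases are summed over all dose and age groups. Use the same wording in Section 1.2 and the SRT charter.

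This takes one sentence in a protocol amendment and one in the charter, with no added data collection. The downside is a somewhat higher chance of a precautionary hold from background COVID-19: the study-wide rather than per-group chances in the last table of the check (at 0.5% assumed risk, 8 percentage points more by n=120). The SRT can lift such a hold after review.

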3.1 Study Design

This Phase 1 study will evaluate the safety, reactogenicity, and immunogenicity of the CV2CoV vaccine in SARS-CoV-2 seropositive healthy adult participants. The study will be conducted in 5 sequential cohorts with dose escalation from 2 μg to 20 μg. A total of up to approximately 180 healthy adult participants will be enrolled, 30 per dose group as indicated in Table 3-1. The 30 participants will be distributed between the younger (≥18 to <65 years old) and older (≥65 years old) age groups, with a minimum of 10 and a maximum of 20 participants in each age group. There will be 3 sentinel participants in each age group within each dose group. A study design schematic is provided in Figure 3-1.

Table 3-1 CV2CoV Study Cohorts, Dose Groups, and Dose Levels

Cohort	Dose Group	Dose Level	Younger Adults ≥18 to <65 Years of Age	Older Adults ≥65 Years of Age	Total Dose Group Sample Size
1	1a	2 μg	$10 \le n \le 20$	$10 \le n \le 20$	30
	1b	4 μg	$10 \le n \le 20$	$10 \le n \le 20$	30
2	2	8 μg	$10 \le n \le 20$	$10 \le n \le 20$	30
3	3	12 μg	$10 \le n \le 20$	$10 \le n \le 20$	30
4	4	16 µg	$10 \le n \le 20$	$10 \le n \le 20$	30
5	5	20 μg	$10 \le n \le 20$	$10 \le n \le 20$	30

Note: The first 3 participants enrolled in each age group within each dose group will be sentinel participants.

The screening period will be up to 14 days, study vaccine administration will occur on Day 1, and participants will have approximately 180 days (6 months) of follow-up after study vaccine administration. Study assessments will be performed in an outpatient setting at qualified study sites.

The study will be open-label. Participants in all cohorts will be screened for eligibility up to 14 days before enrollment. Participants will receive study vaccine according to their cohort (Table 3-1), dose group, and age group; and study visits will proceed according to the SOE (Table 13-1). Participants will be sequentially enrolled to the dose level assigned to their cohort.

Enrollment in each dose cohorts and the progression from vaccination in younger to older adult participants will be staggered based on SRT data review will progress as described in Section 7.8. Holding rules for dosing are described in Section 5.9.

[figure not shown]
Three sentinel participants in the younger age group (Cohort 1) will be enrolled before opening enrollment to the older age group (Cohort 1). Study vaccine administration must be separated by at least 20 hours between sentinel participants in all cohorts and all dose groups. Sentinel participants will remain on site for approximately 4 hours after study vaccination and the remainder of participants in each group will remain on site for approximately 60 minutes after study vaccination for safety monitoring. A safety follow-up telephone call to each sentinel participant in each dose group will be performed on Day 2 (at least 20 hours postvaccination). Vaccination of the next sentinel participant will proceed, provided the safety was acceptable for the prior sentinel(s) per investigator's assessment.

Escalation to the next higher dose cohorts will be based on the SRT review of safety data from the same age group. Enrollment into Cohorts 2 and 3 (8 and 12 μ g, respectively) will begin after the SRT has reviewed Days 1 to 8 safety data (including Day 8 laboratory data) from 3 sentinel participants from the previous dose cohort. Enrollment into Cohorts 4 and 5 (16 μ g and 20 μ g, respectively), will begin after the SRT has reviewed Days 1 to 8 safety data from all participants in the previous dose cohorts.

A first interim analysis of safety and immunogenicity data up to 14 days after study vaccine administration in participants enrolled in Cohorts 1, 2, and 3 will be performed. A second interim analysis of safety and immunogenicity data will be performed 14 days after participants in Cohorts 4 and 5 have received study vaccine.

13 Jun 2022

Figure 3-1 Study Design Figure

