3.2 Rationale for Study Design

This is a Phase 1 first-time-in-human study designed to evaluate the safety, reactogenicity, and immunogenicity of the GSK-CureVac second-generation CV2CoV vaccine to prevent COVID-19 disease caused by existing and new emerging strains of the SARS-CoV-2 virus. This study will evaluate the CV2CoV vaccine in a booster vaccination setting. The study comprises an adult population of participants who have received a documented full primary vaccination series (2 doses only) with a licensed or authorized mRNA COVID-19 vaccine (only Moderna or Pfizer vaccines). The second-generation vaccines are based on the firstgeneration CVnCoV vaccine, for which efficacy and safety data have been collected in the ongoing Phase 2b/3 study (NCT04652102). The rationale for evaluation of doses from 2 to 20 µg is based on the following: 1) The data from this study will support decisions as to whether the candidate vaccine should be further evaluated in advanced phase clinical trials. 2) The data from this study will guide dose selection. 3) The proposed study will support development of the platform. Specifically, if the CV2CoV monovalent candidate induces robust immune responses with an acceptable safety profile, there may be potential to develop future multivalent vaccines to prevent COVID-19 disease based on this platform. The rationale for including older adults in this study is because this age group is at increased risk for severe COVID-19. In addition, the efficacy of the CVnCoV vaccine was lower in older adults than in younger adults < 65 years of age. Thus, safety and immunogenicity data on CV2CoV in this age group will be critical to guiding decisions on whether the CV2CoV vaccine candidate should be advanced further in development.

The starting doses of the CV2CoV vaccine are 2 μ g and 4 μ g in Cohort 1. These starting doses are based on previously tested doses for the first-generation CVnCoV vaccine.

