The maximum planned dose of the CV2CoV vaccine is 20 µg in the present study. In the Phase 1 study, the reactogenicity profile of the first-generation CVnCoV vaccine was dose-dependent from 2 µg to 20 µg. Solicited reactions were more commonly systemic with a frequency of reports generally similar after the administration of the first and the second dose (except for 8 µg and 16 µg). The severity of systemic solicited events increased with dosages with an overall rate of of participants reporting a Grade 3 event. However, Grade 3 solicited events were mostly short-lived and self-limiting, eg, Grade 3 AEs only lasted for 1 day and, 1 participant reported a Grade 3 myalgia after the second dose for 3 consecutive days and resolved on the fourth day. Adherence of participants

to administration of the second dose remained very high, even for the higher doses. Until 24 October 2021, no vaccine-related SAEs, AESIs, or fatalities were reported for any dose in the Phase 1 study. Increases in frequency or severity were not observed for Grade 3 solicited AEs in the later clinical phases with larger sample sizes.

Risk to study participants will be mitigated in several ways:

- 1) A stagger will occur between the younger and older adults based on SRT review of Days 1 to 8 safety data (including Day 8 laboratory data) from 3 sentinels (Cohort 1).
- 2) Each sentinel will be called at Day 2 (at least 20 hours postvaccination) to monitor their safety postvaccination prior to vaccination of the next sentinel.
- 3) The SRT will review Days 1 to 8 safety data (including Day 8 laboratory data) from 3 sentinels in each dose cohort (Cohorts 1-5) prior to expansion in the same dose cohort.
- 4) The SRT will review Days 1 to 8 safety data (including Day 8 laboratory data) from 3 sentinels prior to escalation to the next higher dose cohort (Cohorts 1-3).
- 5) The SRT will review data from the entire dose cohort prior to escalation to the next higher dose cohort (Cohorts 4-5).
- 6) The SRT will continue to review all available safety data to determine study progression.
- 7) Study holding rules have been specifically predefined so that the study will be fittingly put on hold pending the review of all accumulated safety data by the SRT and to decide whether expansion of vaccination and escalation through the higher dosages may continue.

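### Two escalation gates are stated inconsistently: how many Cohort 1 sentinels come before older adults, and whose data are needed before 16 and 20 µg

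*Protocol*

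**What the plan says.** **Opening the older group in Cohort 1.** Protocol Section 3.1 says "Three sentinel participants in the younger age group (Cohort 1) will be enrolled before opening enrollment to the older age group (Cohort 1"). Section 3.2 item 1 bases the stagger between age groups on SRT review of Days 1 to 8 "safety data (including Day 8 laboratory data) from 3 sentinels (Cohort 1"). SAP Sections 3.1 and 4.2 repeat the figure of three. Protocol Section 3.1 also says "There will be 3 sentinel participants in each age group within each dose group", and Table 3-1 gives Cohort 1 two dose groups, 1a (2 µg) and 1b (4 µg). Section 7.8 has the SRT review sentinel data for the 2 µg and 4 µg "dose in the younger age groups and make recommendations to open the enrollment in the older age group".

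**Escalating to higher doses.** Section 3.1 says escalation is "based on the SRT review of safety data from the same age group". For 8 and 12 µg it then asks for three sentinels from the previous cohort. For 16 and 20 µg it asks for all participants in the previous cohorts, in the plural. Section 7.8 says, for the later cohorts, "The SRT will review Day 8 safety data for the entire dose group", with 12 µg before 16 µg as its example. Section 3.2 item 4 describes review of data "from 3 sentinels prior to escalation to the next higher dose cohort (Cohorts 1-3"), and item 5 attaches review of the entire cohort to Cohorts 4-5.

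**The concern.** This is a first-in-human escalation, and these gates decide how much safety information exists before older adults or a higher dose are exposed. Read literally, the sections require different amounts.

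Three sentinels for a cohort with two dose groups cannot also be three per dose group. Section 3.1 adds a further gap: it asks only that the three be enrolled, whereas Sections 3.2 and 7.8 require review of their Days 1 to 8 data.

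Before 16 and 20 µg, the text leaves open whether one age group can advance on its own data or must wait for the other. It also leaves open whether the review covers the preceding dose or all lower doses. Two people could each cite the protocol and open a group on materially different evidence.

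**Working it through.** **Inputs.** Three sentinels per age group per dose group, 30 participants per dose group and 10 to 20 per age group (Protocol Section 3.1 and Table 3-1). Dose groups: two in Cohort 1 and one in each of Cohorts 2 to 5. Maximum tolerable rate of severe solicited events: 30% (Section 5.9).

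**Step 1: the plan's own figures.** The chance of at least one event among n participants at rate p is 1 − (1 − p)^n. For n = 30, 1 − 0.95^30 = 78.5% and 1 − 0.90^30 = 95.8%. Both match Protocol Section 7.2.

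**Step 2: sentinel counts.**
- Older-adult gate: 3 as worded in Sections 3.1 and 3.2; 3 × 2 doses = 6 from the per-dose-group rule with Section 7.8.
- Gate to 8 µg: 3 as worded; 3 × 2 doses = 6 for one age group; 3 × 2 doses × 2 ages = 12 for both.

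**Step 3: participants required under each reading of the later gates.**

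| Reading | Before 16 µg | Before 20 µg |
|---|---|---|
| Same age group, preceding dose only | 10–20 | 10–20 |
| Whole preceding dose group | 30 | 30 |
| Same age group, all earlier cohorts | 4 × (10–20) = 40–80 | 5 × (10–20) = 50–100 |
| Everyone in all earlier cohorts | 4 × 30 = 120 | 5 × 30 = 150 |

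Cohorts 1 to 3 hold four dose groups and Cohorts 1 to 4 hold five.

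**Step 4: what those counts can show.** The last column is the one-sided 95% upper limit on the rate when no event is seen, 1 − 0.05^(1/n).

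| n | At least one event, true rate 10% | At least one event, true rate 30% | Upper limit with zero events |
|---|---|---|---|
| 3 | 27.1% | 65.7% | 63.2% |
| 6 | 46.9% | 88.2% | 39.3% |
| 10 | 65.1% | 97.2% | 25.9% |
| 20 | 87.8% | 99.9% | 13.9% |
| 30 | 95.8% | >99.9% | 9.5% |

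These figures assume one common event rate among the participants counted. Six Cohort 1 sentinels would be three at each of two doses, so the 46.9% applies to the pair of doses; at either dose alone it stays 27.1%. Likewise, a count of 120 includes lower doses and says less about 12 µg than 120 participants at 12 µg would.

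**Step 5: the cohort labels in Section 3.2.** Item 3 uses its label for the cohort being reviewed. If items 4 and 5 do the same, item 4 covers 12 to 16 µg on sentinels alone, and item 5 implies a cohort above Cohort 5. If the label is the cohort being entered, item 4 includes Cohort 1, which has no lower cohort. A third reading, steps among Cohorts 1 to 3 and then entry into Cohorts 4 and 5, agrees with the other sections.

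**The case against.** The best defence is that the sections can be read together. Section 3.1 sends both the younger-to-older progression and the enrolment of each cohort to Section 7.8, which names both Cohort 1 doses. The protocol uses the word cohort loosely: Section 7.2 counts six dose-level cohorts and Section 3.1 counts five. So three may be shorthand for three per dose level. On age, the mention of all participants may simply contrast with sentinels, inside a general same-age rule. Section 5.9 and Appendix 3 also apply safety criteria by age group. The design figure is not shown and the SRT charter is a separate document, so either may settle these points in practice.

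Much of this is reasonable, but it does not close the gap. Sections 3.1 and 3.2 never say per dose group, and the SAP repeats the cohort-level wording. Section 7.8 gives no sentinel count and no same-age condition, and it refers to a single dose group where Section 3.1 uses a plural.

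Two stronger readings should be resisted. A reader might infer from Section 3.2 item 4 that 16 µg can open on sentinel data alone. The synopsis, Protocol Sections 3.1 and 7.8 and SAP Section 3.1 all require review of the whole cohort or dose group first, so only the label is at fault. A reader might also infer that one Cohort 1 dose could have no sentinel reviewed before older adults enter, since SAP Section 4.2 randomizes Cohort 1 between two doses. Section 7.8 rules that out by requiring review at both doses, and the documents state no allocation ratio from which to put a probability on it.

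**Conclusion.** The concern holds for two gates. For older adults in Cohort 1, the text supports three sentinels or six, and the gate to 8 µg supports 3, 6 or 12. Before 16 µg, the age and cohort scope supports 10 to 20 participants, 30, or as many as 120; the 20 µg gate has the same ambiguity. In terms of information, that is a 27% against a 47% chance of seeing a 10% event at the first gate, and 65% (lowest same-age count) against 96% (whole dose group) at the later one. With no events, neither 3 nor 6 participants would exclude the protocol's 30% maximum tolerable rate at the one-sided 95% level; 10 or more would.

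This is a defect of wording, not evidence that the escalation scheme is unsafe or that the SRT would act on the smaller count. The 10% rate is the protocol's own illustrative value, and the charter and figure were not available to check.

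**What to change.** Reconcile the synopsis, Protocol Sections 3.1, 3.2 (items 1, 4 and 5) and 7.8, and the SAP. One table would do it, with a row per gate giving the dose group or groups, the age group or groups, and the number of participants whose Day 1 to 8 data the SRT must have reviewed. Three details belong in the same edit:

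- State in Section 3.1 whether enrolment or completed SRT review of the Cohort 1 sentinels opens the older group.
- Relabel Section 3.2 items 4 and 5 so that the cohort being left and the cohort being opened are both named.
- Align the Cohort 4 and 5 gate on Day 8 laboratory data, which SAP Section 3.1 includes and the matching sentence in Protocol Section 3.1 omits.

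The sponsor decides which requirement applies at each gate and should check the result against the SRT charter. The cost is protocol and SAP wording, with no change to the analysis.
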